3.5 Hepatic

Course of Action

Grade 2 events:

- Hold pembrolizumab
- Monitor liver function tests more frequently until returned to baseline values (consider weekly).

- Treat with 0.5-1 mg/kg/day methylprednisolone or oral equivalent and when LFT returns
- to grade 1 or baseline, taper steroids over at least 1 month, consider prophylactic
- antibiotics for opportunistic infections, and resume pembrolizumab per protocol
- Permanently discontinue for inability to reduce corticosteroid dose to 10 mg or less of prednisone or equivalent per day within 12 weeks.
- Permanently discontinue pembrolizumab for patients with liver metastasis who begin treatment with Grade 2 elevation of AST or ALT, and AST or ALT increases 50% relative to baseline and lasts 1 week.

Grade 3 events:

- Discontinue pembrolizumab when AST or ALT >5.0 times ULN and/or total bilirubin >3.0 times ULN.
- Consider appropriate consultation and liver biopsy to establish etiology of hepatic injury, if necessary
- Treat with high-dose intravenous glucocorticosteroids for 24 to 48 hours.
 - When symptoms improve to Grade 1 or less, a steroid taper with dexamethasone 4 mg every 4 hours or prednisone at 1 to 2 mg/kg should be started and continued over no less than 4 weeks.
- If serum transaminase levels do not decrease 48 hours after initiation of systemic steroids, oral mycophenolate mofetil 500 mg every 12 hours may be given. Infliximab is not recommended due to its potential for hepatotoxicity.
- Several courses of steroid tapering may be necessary as symptoms may worsen when the steroid dose is decreased.
- Permanently discontinue for inability to reduce corticosteroid dose to 10 mg or less of prednisone or equivalent per day within 12 weeks.

Grade 4 events:

- Permanently discontinue pembrolizumab
- Manage patient as per Grade 3 above

A2.6 Neurologic

All attempts should be made to rule out other causes such as metastatic disease, other medications or infectious causes.

Course of Action

Grade 2 events:

Moderate (Grade 2) - consider withholding pembrolizumab.

- Consider treatment with prednisone 1-2 mg/kg p.a. daily as appropriate
- Consider Neurology consultation. Consider biopsy for confirmation of diagnosis.
- Permanently discontinue for inability to reduce corticosteroid dose to 10 mg or less of prednisone or equivalent per day within 12 weeks.

Grade 3 and 4 events:

- Discontinue pembrolizumab
- · Obtain neurology consultation. Consider biopsy for confirmation of diagnosis
- Treat with systemic corticosteroids at a dose of 1 to 2 mg/kg prednisone or equivalent once per day. If condition worsens consider IVIG or other immunosuppressive therapies as per local guidelines
- When symptoms improve to Grade 1 or less, steroid taper should be started and continued over no less than 4 weeks.

A2.7 Ocular

All attempts should be made to rule out other causes such as metastatic disease, infection or other ocular disease (e.g. glaucoma or cataracts). However the AE should be reported regardless of etiology.

Course of Action

Grade 2 events:

- Evaluation by an ophthalmologist is strongly recommended.
- Treat with topical steroids such as 1% prednisolone acetate suspension and iridocyclitics.
- Discontinue pembrolizumab as per protocol if symptoms persist despite treatment with topical immunosuppressive therapy.

Grade 3 events:

- Evaluation by an ophthalmologist is strongly recommended
- Hold pembrolizumab and consider permanent discontinuation as per specific protocol quidance.
- Treat with systemic corticosteroids such as prednisone at a dose of 1 to 2 mg/kg per day.
 - o When symptoms improve to Grade 1 or less, steroid taper should be started and continued over no less than 4 weeks.
- Permanently discontinue for inability to reduce corticosteroid dose to 10 mg or less of prednisone or equivalent per day within 12 weeks.

Grade 4 events:

- Evaluation by an ophthalmologist is strongly recommended
- · Permanently discontinue pembrolizumab.
- Treat with corticosteroids as per Grade 3 above

A2.8 Renal

All attempts should be made to rule out other causes such as obstructive uropathy, progression of disease, or injury due to other chemotherapy agents. A renal consultation is recommended. However the AE should be reported regardless of etiology.

Course of Action

Grade 2 events:

- Hold pembrolizumab
- Treatment with prednisone 1-2 mg/kg p.o. daily.
- Permanently discontinue for inability to reduce corticosteroid dose to 10 mg or less of prednisone or equivalent per day within 12 weeks.

Grade 3-4 events:

- Discontinue pembrolizumab
- · Renal consultation with consideration of ultrasound and/or biopsy as appropriate
- Treat with systemic corticosteroids at a dose of 1 to 2 mg/kg prednisone IV or equivalent once per day.
 - o When symptoms improve to Grade 1 or less, steroid taper should be started and continued over no less than 4 weeks.

A2.9 Skin - Rash and Pruritus

Course of Action

Grade 2 events:

- Symptomatic treatment should be given such as topical glucocorticosteroids (e.g., betamethasone 0.1% cream or hydrocortisone 1%) or urea-containing creams in combination with oral antipruritics (e.g., diphenhydramine HCl or hydroxyzine HCl).
- Treatment with oral steroids is at physician's discretion for Grade 2 events.

Grade 3 events:

- Hold pembrolizumab.
- Consider Dermatology Consultation and biopsy for confirmation of diagnosis.

- Treatment with oral steroids is recommended, starting with 1 mg/kg prednisone or equivalent once per day or dexamethasone 4 mg four times orally daily.
 - o When symptoms improve to Grade 1 or less, steroid taper should be started and continued over no less than 4 weeks.
- Permanently discontinue for inability to reduce corticosteroid dose to 10 mg or less of prednisone or equivalent per day within 12 weeks.

Grade 4 events:

- Permanently discontinue pembrolizumab.
- Dermatology consultation and consideration of biopsy and clinical dermatology photograph.
- Initiate steroids at 1 to 2 mg/kg prednisone or equivalent.
 - o When symptoms improve to Grade 1 or less, steroid taper should be started and continued over no less than 4 weeks.

A2.10 Other

All attempts should be made to rule out other causes. Therapeutic specialists should be consulted as appropriate.

Course of Action

Grade 2 events or Grade 1 events that do not improve with symptomatic treatment:

- Withhold pembrolizumab.
- Systemic corticosteroids may be indicated.
- Consider biopsy for confirmation of diagnosis.
- If pembrolizumab held and corticosteroid required, manage as per grade 3 below.

Grade 3 events:

- Hold pembrolizumab
- Treat with systemic corticosteroids at a dose of 1 to 2 mg/kg prednisone or equivalent once per day.
- When symptoms improve to Grade 1 or less, steroid taper should be started and continued over no less than 4 weeks.
- Permanently discontinue for inability to reduce corticosteroid dose to 10 mg or less
 of prednisone or equivalent per day within 12 weeks. Otherwise, pembrolizumab
 treatment may be restarted and the dose modified as specified in the protocol

Grade 4 events:

 Treat with systemic corticosteroids at a dose of 1 to 2 mg/kg prednisone or equivalent once per day.

• Discontinue pembrolizumab

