11.4.1 Epacadostat

Dose reductions/Interruptions - Epacadostat

In some circumstances, it may be necessary to temporarily interrupt both study treatments as a result of AEs that may have an unclear relationship to study drug. If an interruption is necessary both study treatments should be interrupted.

Any interruptions of> 2 weeks or for LFT abnormalities must be discussed with the medical monitor before resuming treatment. Treatment with both study drugs should be withheld for drug-related Grade 4 hematologic toxicities, nonhematological toxicity Grade 3 (including laboratory abnormalities), and severe or life-threatening AEs.

Epacadostat may be dose reduced according to the guidelines and dose levels described in Table 14.

Dosing interruptions may be permitted in the case of medical/surgical events or logistical reasons not related to study therapy (eg, elective surgery, unrelated medical events,

subject vacation, and/or holidays). Subjects will be placed back on study therapy within 3 weeks of the scheduled interruption. The reason for interruption should be documented in the subject's study record.

For patients who do not tolerate the RP2D of epacadostat in combination with pembrolizumab, three dose reductions are permitted (Table 14) in order to allow the patient to continue on study drug. The following guidelines need to be applied and these changes must be recorded on the Dosage Administration Record. Please refer to Table 15 for dose reduction steps and criteria for interruption and re-initiation of epacadostat for drug-related toxicities. Doses held during the study will not be made up. When toxicity that resulted in a dose reduction improves to grade 1 or less, the dose can be re-escalated at the investigators discretion provided there are no other concomitant toxicities.

Table 14 Dose Modification Algorithm for Adverse Events Associated with Epacadostat

Epacadostat Dose Levels	Dose Level 1 (starting dose)	Dose Level -1	Dose Level -2
Actual Dose	100mg bid	50mg bid	25mg bid

Table 15. Dose Modification Guidelines for Epacadostat Related Adverse Effects without Immune Etiology

Toxicity	Grade	Hold	Timing for	Dose for	Discontinue
		Treatment	Treatment	Treatment	Subject (after
		(Y/N)	Restart	Restart	discussion with PI)
Hematologic	1,2,3	No	N/A	N/A	N/A
Toxicity					
	4	Yes	Permanently discontinue treatment	N/A	Permanently discontinue study treatment
Non Hematologic Toxicity	1	No	N/A	N/A	N/A

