Immune-related AEs	Toxicity Grade or Conditions (CTCAEv4.0)	Study Medication	Action Taken with Study Medication	irAE Management with Corticosteroid and/or Other Therapies	Monitor and Follow-up
			1 dose level. Not Related: Same dose level.		• If Grade 4 lipase/amylase elevation is asymptomatic and abdominal imaging suggests no pathology, study drug administration dosing may continue with medical monitor approval.
		Pembrolizuma b	Withhold until Grade 0- 1	Based on severity of AE administer corticosteroid	Ensure adequate evaluation to confirm
	Immune-related		Withhold until Grade 0-1	s	etiology or exclude other causes
All Other Immune-related AEs		Epacadostat	Related: Reduce by 1 dose level.		
		Not Related: Same dose level.			
	Grade 4 or recurrent	Pembrolizuma b	Permanent! y discontinue		
	Grade 3	Epacadostat	Permanent! y discontinue		

				irAE	
Immuno volotod	Toxicity Grade or	Cturdu	Action Taken with	Management	Manitarand
Immune-related	Grade or	Study	i aken with	with	Monitor and
AEs	Conditions	Medication	Study	Corticosteroid	Follow-up
	(CTCAEv4.0)		Medication	and/or Other	
	,			Therapies	

General Instructions:

- 1. Corticosteroid taper should be initiated upon AE improving to Grade 1 or less and continue to taper over at least 4 weeks.
- 2. For situations where pembrolizumab and epacadostat have been withheld, pembrolizumab and epacadostat/placebo can be resumed after AE has been reduced to Grade 1 or O and corticosteroid has been tapered. Pembrolizumab and epacadostat/placebo should be permanently discontinued if AE does not resolve within 12 weeks of last dose or corticosteroids cannot be reduced to:S 10 mg prednisone or equivalent per day within 12 weeks.
- 3. For severe and life-threatening irAEs, IV corticosteroid should be initiated first followed by oral steroid. Other immunosuppressive treatment should be initiated ifirAEs cannot be controlled by corticosteroids.
- 4. Pembrolizumab should be permanently discontinued if Stevens Johnson Syndrome (SJS) or Toxic Epidermal Necrolysis (TEN) occurs.

NOTES:

- 1. Withhold OR permanently discontinue pembrolizumab + epacadostat at the discretion of the Investigator.
- 2. For participants with Grade 3 or 4 immune-related endocrinopathy where withholding of pembrolizumab and epacadostat is required, pembrolizumab and epacadostat may be resumed when AE resolves to :S Grade 2 and is controlled with hormonal replacement therapy or achieved metabolic control (in case of TIDM)

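### Table 16 and Appendix B give different permanent-stop rules for pembrolizumab in two cases, and no sentence expressly says which prevails

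*Combined protocol and SAP*

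**What the plan says.** **Neurologic events.** Table 16 has rows for pneumonitis, colitis, liver tests, diabetes, hypophysitis, thyroid, kidney, rash and amylase/lipase, but none for neurologic events. These therefore fall under *All Other Immune-related AEs*, where the permanent stop is for "Grade 4 or recurrent" grade 3. Below that level both drugs are withheld until grade 0-1. General Instruction 2 then says that "pembrolizumab and epacadostat/placebo can be resumed after AE has been reduced to Grade 1 or O and corticosteroid has been tapered". Appendix B A2.6 gives one instruction for neurologic grade 3 and 4 events together: "discontinue pembrolizumab". By contrast, Appendix B A2.10 (*Other*) holds at grade 3, after which "treatment may be restarted and the dose modified as specified in the protocol" provided steroids can be reduced in time.

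**Liver tests.** Table 2 admits patients with liver metastases with AST/ALT up to 5 x ULN. The asterisk footnote to Table 16 lets those who start at grade 2 stay on the same dose, with no need to withhold, as long as values remain grade 2. If values fall to grade 0-1 and later return to grade 2, the ordinary liver row applies. Appendix B, Hepatic, permanently stops pembrolizumab in patients with liver metastases who "begin treatment with Grade 2 elevation of AST or ALT, and AST or ALT increases 50% relative to baseline and lasts 1 week". Its grade 3 rule reads "Discontinue pembrolizumab when AST or ALT >5.0 times ULN and/or total bilirubin >3.0 times ULN".

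**Which source governs.** Section 9.1 sends dose modification to section 11.4. The heading of section 11.4 covers withholding, restarting and permanent discontinuation, and section 11.4.2 makes withholding of pembrolizumab according to Table 16 mandatory. Sections 9.5 and 11.5 also direct the reader to Appendix B for managing toxicity.

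**The concern.** An investigator who follows section 11.4 as written could re-dose a patient after a grade 3 neurologic event, or keep dosing through a sustained AST/ALT rise, although the protocol's own appendix says to stop for good. Conversely, two investigators could treat the same event differently and both point to the protocol.

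The neurologic case is not remote. The safety text before Table 9 reports five treatment-related discontinuations among 62 phase 1 subjects on this combination. One was a grade 3 aseptic meningitis and one a grade 2 nervous system disorder. No event rate for this trial follows from that.

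What is at stake is patient safety in individual cases and consistent handling and reporting of discontinuations. The response endpoint, sample size and decision rule are untouched.

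**Working it through.** **Neurologic case, side by side**

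| Event | Table 16, *All Other* rows | Appendix B A2.6 |
|---|---|---|
| First grade 3 | Withhold to grade 0-1, may resume | Discontinue |
| Recurrent grade 3 | Permanent stop | Discontinue |
| Grade 4 | Permanent stop | Discontinue |

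1. The sources differ only in the first line.
2. The grade label of the withhold row is damaged in the extracted text. That it covers a first grade 3 event is inferred from the row beneath it and from section 11.4.1, which withholds both drugs for "nonhematological toxicity Grade 3 (including laboratory abnormalities), and severe or life-threatening AEs".
3. Appendix B separates hold from discontinue throughout, and A2.10 allows restart after grade 3. The stricter neurologic line therefore looks intended.
4. Section 11.4.1 requires discussion with the medical monitor before resuming after an interruption of more than 2 weeks. Steroid-treated events may well reach that, since General Instruction 1 has the steroid "continue to taper over at least 4 weeks". The discussion comes with no stopping criterion.

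**Hepatic case**

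Inputs: the grade 3 threshold is above 5.0 x ULN (Appendix B, Hepatic). The rise is 50% over baseline lasting 1 week, read as at least 50% and at least 1 week because comparison signs appear to be lost. The lower bound of grade 2 is not in the documents, so 3.0 and 2.5 x ULN are both taken as assumptions.

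1. For a baseline *b*, a 50% rise gives 1.5*b*. It stays grade 2 only if 1.5*b* <= 5.0, so *b* <= 5.0/1.5 = 3.33 x ULN.
2. Example below the limit: *b* = 3.2 gives 1.5 x 3.2 = 4.8. This is still grade 2: the footnote permits dosing and Appendix B stops.
3. Example above the limit: *b* = 3.5 gives 1.5 x 3.5 = 5.25. This is grade 3, and both sources stop permanently.
4. Width of the window as a share of the grade 2 range:
   - lower bound 3.0: (3.33 - 3.0)/(5.0 - 3.0) = 0.167, about one sixth;
   - lower bound 2.5: (3.33 - 2.5)/(5.0 - 2.5) = 0.333, about one third.

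These are shares of a laboratory range, not of patients.

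5. Appendix B applies only to events judged related to pembrolizumab, so an unchanged baseline value raises no conflict.
6. Section 10.3 allows a new dose only once grade 2 non-hematologic events have resolved to grade 1, but exempts laboratory values that are not clinically significant. It can therefore block a dose in this window if the rise is judged clinically significant, but it sets no permanent stop. The medical-monitor step concerns resuming after an interruption, and the footnote involves none.

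**The case against.** The strongest reply is that the protocol already has a hierarchy. Section 9.1, the heading of section 11.4 and the mandatory wording of section 11.4.2 all point to Table 16. Appendix B is presented as suggested supportive care, section 11.5 applies it as the treating investigator sees fit, and several of its lines defer to the protocol. A reader might infer from the mismatch that nothing indicates which source applies. The documents do not support that: the lean towards Table 16 is clear.

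It stops short of precedence, however. Section 11.4.2 speaks of withholding, not of permanent discontinuation. The care measures in Table 16 are also introduced as suggested. The grade 3-4 neurologic line and the 50%-rise line are plain directives without deference to the protocol.

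Second, the hepatic texts can be read together, as a general permission with a narrower stop inside it. That stands in part: an investigator who stops breaches nothing. It does not help the one who relies on the footnote alone. A reader might also infer that such a patient could be dosed without any check, but section 10.3 does not allow so strong a statement.

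Third, a reader might subtract the 4-week taper from the limit of about 9 weeks since the last dose in section 11.0, and conclude that restart after a steroid-treated neurologic event requires recovery within 5 weeks. Section 9.5 lets dosing resume once the steroid is down to 10 mg prednisone daily, before the taper need be complete, so no such limit is firm.

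**Conclusion.** Both differences are in the text. The neurologic one concerns a first grade 3 event only, and rests on an inferred grade label for the withhold row. The hepatic one is confined to liver-metastasis patients who enter at grade 2 with a baseline of at most 3.33 x ULN and then have a sustained, drug-related 50% rise that stays grade 2. That window is one sixth to one third of the grade 2 range under the two assumed lower bounds, and section 10.3 may narrow it further in practice.

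The text favours Table 16 without expressly placing it above Appendix B. Following it as written therefore permits dosing that the appendix would end. The point is minor: no endpoint, sample size or decision rule changes, and no event rate can be given from the documents. Section 16.3 describes the study as completed; if dosing is finished, only reporting is affected.

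**What to change.** Subject to clinical confirmation of the stricter rules:

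- add a neurologic row to Table 16 with permanent discontinuation at grade 3 or 4;
- add the stop for a 50% rise lasting 1 week to the liver-metastasis footnote of Table 16;
- state in section 11.4 that Table 16, as amended, governs dose actions where Appendix B differs.

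The cost is amendment wording and possibly a few more permanent stops. If dosing is finished, no amendment is needed: report, for any affected neurologic or hepatic event, which rule was applied.
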